19.3 Analysis Sets

Safety Population Analysis Set (SP): The SP analysis set will consist of all enrolled subjects who have had insertion of the study catheter, regardless of energy delivery.

Modified Intention-To-Treat (mITT) Analysis Set: The mITT analysis set will consist of enrolled subjects who meet eligibility criteria and have had insertion of the study catheter.

Per Protocol (PP) Analysis Set: The PP analysis set will consist of subjects who satisfy the following criteria:

- Have undergone ablation using PF and/or RF energy via the investigational ablation system per CIP
- Are treated for the study-related arrhythmia
- Are enrolled and without major CIP deviation that would affect the scientific integrity of the safety and effectiveness, including but not limited to the following:
 - Subjects found not meeting eligibility criteria
 - Failure to check for entrance block for each targeted PV after adenosine/isoproterenol challenge.

- Use of the investigational ablation system outside the PV region. A CTI line for documented typical AFL identified prior to or during the procedure using investigational system or commercial RF devices to complete the procedure is allowed during index or repeat ablation procedure (within blanking). For the treatment of arrhythmia outside the PV region, using commercial RF devices to complete the procedure is allowed. However, subjects using commercial RF devices for the non-PV regions and/or CTI lines will be excluded from the 12-month effectiveness analysis.
- Missing all CIP specified electrocardiographic effectiveness monitoring

Neurological Assessment (NA) Analysis Set: The NA analysis set will include 30 subjects who have had pre-and post-index-ablation procedure MRI and neurological assessments completed. Subjects with no pre-index ablation procedure MRI assessment and no lesions observed on post-MRI assessment will be included for analysis.

Esophageal Endoscopy (EE) Analysis Set: The EE analysis set will include 30 subjects who have had a readable 1 to 3 days post index-ablation procedure esophageal endoscopy assessment.

Cardiac CT/MRA Analysis Set: The CT/MRA analysis set will include 30 subjects who have readable outcomes at baseline and 3 months.

PVI Durability Analysis Set: The PVI durability analysis set will include 30 subjects who have readable electro-anatomical mapping at index ablation procedure and 75 days (+/-15 days) post index ablation procedure.

19.4 Analyses to be Conducted

19.4.1 General Conventions

Standard descriptive summaries for continuous data include the number of observations with data, number of observations with missing data, mean, standard deviation, median, 25% percentile, 75% percentile, minimum, and maximum values. For categorical data, the count and percent will be provided. Percentages will be based on the number of subjects without missing data.

19.4.2 Subject Disposition

Disposition and accountability of the study subjects will be summarized descriptively for the subject categories defined as following,

Enrolled Subjects: Patients who sign the ICF.

Excluded Subjects: Subjects who are enrolled but never undergo insertion of the study catheter. Excluded subjects will be subjected to safety event reporting between ICF signature and date of exclusion. Subjects who signed the ICF but are found to be ineligible prior to insertion of the catheter are also considered as excluded.

Evaluable Subjects: All enrolled subjects who have the study catheter inserted.

Discontinued Subjects: Evaluable subjects who have the catheter inserted, but do not undergo ablation (i.e., no energy is delivered with the study catheter).

- Discontinued subjects will remain in follow-up for 3-months post catheter insertion.
- Discontinued subset subjects are not subjected to the additional subset assessments (esophageal, neurological, PV and PVI durability).

- If an SAE is reported for a discontinued subject, the subject will be followed until event resolution (with or without sequelae), stabilization, or until the event is adequately explained.

Lost to Follow-up Subjects: Evaluable subjects of which contact is lost after most recent visit (despite 3 documented attempts to contact the subject).

Withdrawn / Early Termination Subjects: Subjects who withdraw consent for study participation or are withdrawn by the investigator, are terminated from the study prior to completion of all follow-up visits.

Completed Subjects: Enrolled subjects who have not been excluded, discontinued, withdrawn, terminated early, or lost-to-follow-up from the study prior to the final study visit.

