6.2 Additional Objective

The additional objectives of this study are to evaluate procedural data, quality of life and the incidence of (procedure and/or device related) serious adverse events during and after procedure up to 12 months.

7 Study design and Endpoints

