13.3.3 Study Ablation Procedure Sequence & Guidelines

Subjects will arrive to the electrophysiology (EP) laboratory for their ablation procedure and will undergo preparation for the procedure per the hospital's standard protocol (discretion of investigator).

PREPARATION of the ablation procedure:

- Anesthesia or sedation should be delivered per standard EP lab procedure. It is highly recommended to ensure presence of an anesthesiologist during the procedures.
- **REQUIRED:** Placement of two indifferent electrodes on the patient prior to mapping.
- Esophageal monitoring/localization (investigator discretion) with CARTOSOUND® and/or ICE, barium swallow or temperature probe (CIRCA™ or Single Thermistor™ probes ONLY).
- CARTO™ Respiratory gating recommended (unless using Jet Ventilation).
- Introduce an Intracardiac Echo (ICE) probe to review LA anatomy and PVs (at investigator discretion).
- Diagnostic catheter placement:
 - Coronary sinus catheter in the CS for pacing purposes is recommended
 - Other catheters may be placed at the discretion of investigator
- **REQUIRED:** Administration of heparin bolus prior to or immediately following transseptal puncture.
- A double or single transseptal puncture should be performed per standard EP lab (at the discretion of the investigator).
- Cardioversion if subject is in AF (at discretion of investigator).

MAPPING prior to the ablation procedure:

- **REQUIRED:** Creation of a left atrial anatomical map, including PV anatomy prior to ablation, utilizing a multi-electrode BWI mapping catheter.
- Additional imaging techniques such as 3D rotational angio (at investigator discretion), or CT integration can be used to supplement the map.
- A pre-ablation paced activation and bi-polar voltage map may be created at physician discretion and if SOC.
- **For subjects participating in PVI durability subset:**
 - **REQUIRED:** creation of paced activation map and bipolar voltage map, utilizing a BWI multi-electrode mapping catheter.
- Pace the phrenic nerve prior to ablation in the region of the right sided PV's in order to evaluate the proximity. NOTE: in case of deep sedation a fluoroscopic evaluation of the diaphragm may be used.

ABLATION Procedure:

- **REQUIRED:** Confirmation of ACT \geq 300 seconds PRIOR to start ablation with investigational catheter and systematic anticoagulation with heparin should be administrated.
 - ACT must be targeted to be maintained \geq 300 seconds throughout the ablation.

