13.3.5 Data Collection during Study Ablation Procedure

The following information will be collected during the procedure, including but not limited to:

Technical parameters are collected via CARTO™ datafiles and generator files, including but not limited to:

- Number of PF/RF applications
- Energy delivered
- PF/RF application time
- Ablation settings used
- Ablation information will be collected in the CARTO™ 3 system and investigational Generator
- Contact force values

Other procedural parameters are collected via Electronic Data Capture (EDC), including but not limited to:

- Use of a non-study catheter for PVI
- Number of PF/RF applications per left and right PV per left and right PV
- Number of PF/RF applications per target PV and by subject
- Number of PF/RF applications required with a non-study catheter
- PVI confirmed with BWI multi-electrode mapping catheter
- PV acute reconnection (early or dormant)
- Procedure time (from first femoral puncture to last catheter out)
- Mapping time (start mapping - end mapping)
- Total fluoroscopy time
- Total study catheter LA dwell time (from first study catheter insertion in LA until study catheter removal from LA)
- ECG data
- Total fluid delivered via study catheter
- Total fluid delivered via intravenous line (if captured)
- Fluid output (if captured)
- Device deficiency information (if applicable)
- Procedural medication (paralytics)
- Use of paralytics and type of anesthesia

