19.4.6 Additional Endpoint Analyses

No formal statistical hypothesis and inferential statistics will be formulated and performed for the additional endpoints. Additional safety endpoints will be analyzed in SP and mITT analysis sets. Effectiveness endpoints and procedural data will be analyzed in the PP and mITT analysis sets respectively. NA, EE, CT/MRA, and PVI Durability endpoints will be analyzed in the NA, EE, CT/MRA, and PVI Durability analysis sets, correspondingly. Details of the analyses will be elaborated in the SAP.

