### 5. Analysis Sets

Analysis sets in this study are defined as the following:

- **Safety Population Analysis Set (SP):** The SP analysis set will include all enrolled subjects who have had the study catheter inserted, regardless of whether energy is delivered or not.
- **Modified Intention-To-Treat (mITT) Analysis Set:** The mITT analysis set will include enrolled subjects who meet the eligibility criteria and have had the study catheter inserted, regardless of whether energy is delivered or not.
- **Per Protocol (PP) Analysis Set:** the PP analysis set will only include enrolled eligible subjects who have undergone the ablation procedure using PF and/or RF energy via the investigational ablation system for the study-related arrhythmia. Subjects who have major protocol deviations that could affect the scientific integrity of the safety and effectiveness will be excluded from the PP analysis set, which includes (but not limited to):
  - Subjects who are found not to meet the eligibility criteria after undergoing the ablation procedure.
  - Subjects who fail in checking entrance block for each targeted PV after adenosine/isoproterenol challenge.
  - Subjects who undergo ablation using the investigational ablation system outside the PV/CTI region
  - Subjects who miss all CIP specified electrocardiographic effectiveness monitoring records.

- **Neurological Assessment (NA) Analysis Set:** The NA analysis set will include all NA subset subjects who have met the additional eligibility criteria specific for the NA subset and have had pre- and post-index-ablation procedure MRI and neurological assessments completed. Subjects who do not have a pre-index ablation procedure MRI assessment but have no lesions observed on post-procedure MRI assessment will still be included for analysis.
- **Esophageal Endoscopy (EE) Analysis Set:** The EE analysis set will include all EE subset subjects who have met the additional eligibility criteria specific for the EE subset and had a readable result of esophageal endoscopy assessment that is done within 1 to 3 days after the index-ablation procedure. Only subjects who have a readable esophageal endoscopy assessment within the specified time frame will be included in analyses for the EE endpoints.

*Note: Endoscopy preferable between 1 day to 3 days (72hours) post procedure. For procedures on Friday, a window of a maximum of 96 hours is justified.*

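### Subjects who had vascular access but no study catheter inserted appear in no planned safety summary, and the rule that ends their event reporting at exclusion conflicts with the general adverse event rules

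*Protocol*

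**What the plan says.** Protocol 19.3 defines the two sets used for safety. For SP: "The SP analysis set will consist of all enrolled subjects who have had insertion of the study catheter, regardless of energy delivery". For mITT: "The mITT analysis set will consist of enrolled subjects who meet eligibility criteria and have had insertion of the study catheter". SAP section 5 keeps the same entry point: "The SP analysis set will include all enrolled subjects who have had the study catheter inserted, regardless of whether energy is delivered or not".

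Primary safety is tested in mITT (protocol 19.4.4, SAP 7.5.1), and its sensitivity analyses use SP and mITT (SAP 7.6.1). For the other safety endpoints, protocol 19.4.6 says: "Additional safety endpoints will be analyzed in SP and mITT analysis sets". SAP 7.11.2 agrees. Only disposition and baseline data are summarised for all enrolled subjects (protocol 19.4.3, SAP 7.2 and 7.3).

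Protocol 19.4.2 classes anyone enrolled who never has the study catheter inserted as Excluded, whatever the reason, and adds: "Excluded subjects will be subjected to safety event reporting between ICF signature and date of exclusion". Discontinued subjects (catheter in, no energy delivered) are followed for 3 months.

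In protocol 13.3.3 the heparin bolus and transseptal puncture belong to the preparation stage. A mapping stage follows, with this required step: "Creation of a left atrial anatomical map, including PV anatomy prior to ablation". Mapping is done with a separate multi-electrode catheter. The study catheter is introduced only in the ablation stage. Section 13.3.5 times the procedure from the first femoral puncture.

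**The concern.** The invasive part of the visit begins before the point at which a subject can enter a safety set. Two kinds of subject fall into the interval: those whose procedure is stopped by a complication of access, transseptal puncture or mapping, and those excluded at that stage for another reason. For the second kind the protocol itself provides routes. Section 13.2.1 excludes subjects whose left atrial or ejection fraction re-measurement during the index procedure fails the criteria. Section 13.3.3 excludes subjects found, before study-catheter insertion, to need ablation outside the pulmonary vein and cavotricuspid regions; they are switched to a commercial system.

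At stake is the completeness of the safety account. The additional objective in protocol 6.2 covers "the incidence of (procedure and/or device related) serious adverse events during and after procedure up to 12 months", and several listed primary adverse events, such as tamponade and major vascular access complications, can arise from steps that precede the study catheter. A reader of the study report could not tell whether any such events occurred.

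**Working it through.** No figure in the plan depends on this point, so the check is mainly a comparison of sections.

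**1. The plan's own safety figure.** Inputs from protocol 19.2: 135 subjects, 5% attrition, goal 12%, assumed rate 5%, one-sided exact test at 0.025. Evaluable n = 135 × 0.95 = 128.25, taken as 128. The largest x with P(X ≤ x | 128, 0.12) ≤ 0.025 is 8 (probability 0.0240). Power = P(X ≤ 8 | 128, 0.05) = 80.8%. The stated power above 80% reproduces.

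**2. Who is counted and for how long.**

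| How far the subject got | Category | SP / mITT | Event reporting under 19.4.2 and the visit schedule |
|---|---|---|---|
| Access, transseptal puncture or mapping; study catheter not inserted | Excluded | neither | consent to exclusion |
| Study catheter inserted, no energy | Discontinued | SP; mITT if eligible | 3 months; SAEs until resolved, stable or explained |
| Study catheter inserted, energy delivered | Evaluable | SP; mITT if eligible | 12 months (3 months for one case in 13.3.3) |

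SP and mITT differ only in eligibility. Repeating an analysis in SP therefore does not bring back the first row.

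**3. Section 19.4.2 against section 14.** Section 14.3 records reportable events starting at any time after consent and has adverse events followed until resolved, stabilised or explained. Section 14.4.1 runs from consent to the end of the study. Section 19.4.2 stops at exclusion. The event that ends the procedure falls inside both windows and is reported. An event that starts after exclusion, for example a delayed effusion or access-site bleed, is inside section 14 and outside 19.4.2. Section 19.4.2 is also silent on follow-up of events already open in Excluded subjects, though it covers SAEs in Discontinued subjects.

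**4. How many subjects.** The documents give no rate. Table 8 gives tamponade 0.2% to 5% and vascular complications 0.2% to 1.5%, over all stages of the procedure. As a pure assumption, let q be the proportion of procedures started that end before insertion with a primary-type event. With 135 procedures started, the expected count is 135q and the chance of at least one is 1 − (1 − q)^135:
- q = 0: none.
- q = 0.25%: 0.34 expected, 28.7%.
- q = 2%: 2.7 expected, 93.5%.

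Exclusions without a complication (13.2.1, 13.3.3) come on top, and their number is also not given.

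**5. Closeness of the primary limit, for reference.** The exact two-sided 95% upper bound is the 0.975 quantile of Beta(x + 1, n − x):
- 8/128 gives 11.94% and 9/129 gives 12.83%.
- 8/135 gives 11.34% and 9/136 gives 12.19%.

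With 128 subjects in the set, one additional counted event would lower the allowed in-set events from 8 to 7. The chance of passing at a 5% in-set rate would go from 80.8% to 69.0%, a difference of about 12 percentage points, which is the chance of exactly 8 in-set events.

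**The case against.** The strongest defence is the endpoint itself. Protocol 7.3.1 and SAP 7.4.1 limit the primary safety endpoint to index procedures in which the study catheter and generator are used. A procedure that ends before the catheter enters the body is outside that definition, and set entry at insertion matches it. This stands, and it answers an inference a reader might draw from the sections above: that the primary adverse event rate is biased downward. The documents do not show that. The 12% goal was built from composites re-derived from other trials (protocol 5.3), and nothing tells us whether those counted events before device insertion.

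A second tempting inference is that these subjects have no safety reporting at all. That is also wrong. The event that stops the procedure is reported under 19.4.2 and section 14.4. Serious events go to the sponsor within 72 hours, those possibly related to the investigation procedure go to the authorities and ethics committees, and sponsor and data monitoring committee safety review is planned. What is missing is a place in a planned summary and, under 19.4.2, capture of later new events.

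A third is that one such event could decide the trial. The bounds in step 5 are correct, but they matter only if exactly 8 in-set events occur, and they describe a test that should not change. Nor can Table 8 be turned into a rate for this interval: the two maxima sum to 5% + 1.5% = 6.5%, more than the 5% assumed for the whole composite, and its vascular figure is not restricted to major complications.

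**Conclusion.** The structural gap holds. A subject with femoral access, transseptal puncture or mapping but no study catheter inserted is in no planned safety summary. Sections 19.4.2 and 14.3/14.4.1 disagree on new events after exclusion, and the date on which the difference turns is undefined. If that date were set late enough, the reporting gap would shrink; the summary gap would remain.

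The primary mITT test is consistent with its endpoint and needs no change. The number of affected subjects is unknown and may be zero; the range in step 4 is assumed, not documented. This is a cheap improvement to the completeness of the safety report, and no argument against the primary analysis.

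**What to change.** 1. In protocol 19.4.6 and SAP 7.11.2, add a descriptive table of adverse events, serious adverse events and events of the primary type for Excluded subjects in whom vascular access was started. Keep it separate from SP and mITT. Show subjects switched to a commercial system before insertion (13.3.3) on their own row, because their later events may come from a full commercial ablation.
2. In protocol 19.4.2, define the date of exclusion, reconcile the reporting rule with 14.3 and 14.4.1, and keep event reporting open through the 7-day contact for Excluded subjects who had vascular access.
3. If a sensitivity analysis of the primary adverse event rate in all started procedures is added to SAP 7.6.1, count for these Excluded subjects only events arising before any commercial ablation. Without that limit, the rate would mix in events from a different system.

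The cost is one extra table, a 7-day contact for what is likely to be a few subjects, and a safety picture that may look slightly less favourable.

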19.4.3 Demographic and Baseline Characteristics

Subject demographics, medical history, previously failed AADs, active AAD use (still administered) and other baseline data will be summarized descriptively for all enrolled subjects.

19.4.4 Primary Endpoint Analyses and Associated Hypotheses

The number and percentage of primary safety events will be summarized in the mITT analysis set after all study subjects completed the 3-month follow-up. Similarly, the number and percentage of primary acute effectiveness events will be summarized in the PP analysis set after all subjects completed the index ablation procedure. The primary endpoint analysis will be part of the CE mark application dossier.

The PAE rate will be formally compared against a performance goal of 12%. Additionally, the primary effectiveness success rate will be compared to a performance goal of 90%. The primary safety endpoint analysis will be performed in the mITT analysis set and the primary effectiveness analysis will be performed in the PP analysis set.

Primary Safety Endpoint:

The null and alternative hypotheses are:

$H_0: P_s \geq 0.12$ vs. $H_A: P_s < 0.12$,
where P_s denotes the rate of early onset Primary Adverse Events

The primary safety endpoint will be evaluated using an exact test for a binomial proportion at a one-sided significance level of 2.5%. If the upper bound of the exact two-sided 95% confidence interval of the primary safety endpoint rate is less than the performance goal of 12%, the study will be considered to have demonstrated safety.

Primary Effectiveness Endpoint:

The null and alternative hypotheses are:

$H_0: P_E \leq 0.90$ vs. $H_A: P_E > 0.90$,
where P_E denotes the rate of acute effectiveness success

The primary effectiveness endpoint will be evaluated using the exact test for a binomial proportion at a one-sided significance level of 2.5%. If the lower bound of the exact two-sided 95% confidence interval of the primary effectiveness endpoint rate is greater than the performance goal of 90%, the study will be considered to have demonstrated effectiveness.

The study will be declared a success if both primary safety and acute effectiveness endpoints are met. The secondary endpoint will be tested only if the primary endpoints are met.

19.4.4.1 Subgroup Analyses

Subgroup analyses by clinically relevant factors will be performed and details will be provided in SAP.

19.4.5 Secondary Effectiveness Endpoint Analysis

The null and alternative hypotheses are:

$H_0: P_1 \leq 0.50$ vs. $H_A: P_1 > 0.50$,
where P_1 denotes the rate of secondary effectiveness success.

Percentage (%) of subjects with freedom from documented symptomatic and asymptomatic atrial arrhythmia (AF, AT or AFL of unknown origin) episodes based on electrocardiographic data (≥ 30 seconds on arrhythmia monitoring device) during the effectiveness evaluation period (Day 91-Day 365) will be estimated in the PP population at 365 days with the corresponding two-sided 95% exact binomial lower bound. Acute procedural failure (i.e., failure to confirm entrance block with or without touch-up in all PVs except those that are silent and/or cannot be cannulated post procedure) will also be deemed an effectiveness failure. The secondary effectiveness endpoint will be evaluated using the exact test for a binomial proportion at a one-sided significance level of 2.5%. If the lower bound of the exact two-sided 95% confidence interval of the secondary effectiveness endpoint rate is greater than the performance goal of 50%, the study will be considered to have demonstrated effectiveness.

